2.5 Withdrawal from the Study

2.5.1 Reasons for Withdrawal or Termination

Participation in the study is strictly voluntary. Subjects have the right to withdraw from the study at any time and for any reason, without penalty. Site Principal Investigators and/or designees may, at her/their discretion, withdraw a subject from continuing in the study if it is in the subject's best interest, or if the subject is not willing or able to comply with the study requirements. The reason for withdrawal will be documented.

2.5.2 Handling of Subject Withdrawals or Termination

Every effort will be made to undertake protocol-specified safety follow-up procedures to capture protocol specified assessments. An investigator may discontinue or withdraw a participant from the study for the following reasons:

- Significant non-compliance
- If the participant meets an exclusion criterion (either newly developed or not previously recognized) that precludes further study participation
- Subject has completed the study follow-up period
- Death
- Screening Failure

The reason for participant discontinuation or withdrawal from the study will be recorded on the discontinuation/withdrawal Case Report Form (CRF).

A participant will be considered lost to follow-up if a follow up visit is missed and the participant is unable to be contacted by the study site staff following at least three attempts (where possible, three telephone calls and, if necessary, a certified letter to the participant's last known mailing address or local equivalent methods).

3 STUDY PROCEDURES AND SCHEDULE

The frequency of the following assessments will be according to the schedule of study procedures in Appendix 1. Not all the following assessments need to be performed at every visit, only those that the subject is able to perform.

1. 4.1 Medical Information

Medical History: Medical history of participating subjects will be recorded in order to obtain the following data: basic demographic information (sex, ethnicity), past medical history, birth history, surgical history, developmental history, medications and family history. We will also collect time of symptoms onset (e.g., motor, language, etc.) and progression, age at diagnosis and genetic results.

Physical and Neurological Examination: At each visit, a physical exam will be recorded including but not limited to evaluation of the ears, nose, throat, heart, lungs, abdomen, back, and extremities, motor and sensory, and vital signs which will include blood pressure (measured in one arm or, if necessary, one leg, after the subject has been seated for approximately 5 minutes), pulse, temperature, height, weight, and head circumference.

A detailed neurological examination including but not limited to evaluation of cranial nerves, muscle tone, muscle strength, sensation, gait, coordination and deep tendon reflex testing will also be performed. Handheld dynamometry will also be performed during clinic visits in muscles of the upper and lower extremities. The examination is anticipated to take approximately 30 minutes.

3.1 Outcome Measures

CMT Pediatric Scale (CMTPedS): The CMTPedS is a clinical tool used to supplement a neurological examination and capture functionally relevant limitations caused by CMT in the pediatric population. It is intended to have broad application in natural history studies and clinical trials of rehabilitative (e.g., orthoses, stretching, strengthening), pharmacological (e.g., curcumin, anti-progesterone) and surgical (e.g., foot and hand tendon transfer, arthrodesis, hip dysplasia) interventions (3). This scale will be used for subjects aged 5 to 17 years 11 months (less than 18 years).

CMT Infant Scale (CMTInfS): The CMTInfS is a validated clinical tool and requires 20 min to administer and is a reliable and sensitive 15-item functional outcome measure for early onset CMT and related neuropathies. The CMTInfS can be implemented in natural history studies to understand the rate of progression at the earliest stages of disease in preparation for therapeutic trials of early interventions. The CMTPedS involves some difficult items that require advanced levels of comprehension, so high variability is seen in children <4 years of age. Therefore, for children aged 3 years, the CMTInfS may be more sensitive to disease severity and clinical impression.

CMT Neuropathy Score, second version (CMTNSv2): The CMTNSv2 is a validated clinical outcome measure developed for use in clinical trials to monitor disease impairment, severity and progression in affected CMT subjects (4). This scale will be used for subjects 18 years of age or older.

CMT Functional Outcome Measure (CMT-FOM): The CMT-FOM is a performance-based outcome assessment which measures limitations in functional abilities in adults with CMT1A (5). It was based on the validated CMTPedS and further developed using review of the literature, patient interviews and a survey of 407 adults with CMT, and subjects 18 years of age or older.

CMT Health Index (CMTHI): The CMTHI is a disease-specific, patient reported outcome measure designed to capture the disease burden of inherited neuropathies, in the context of a clinical trial (6). This scale will be used for subjects 18 years of age or older.

Vineland Adaptive Behavior Scale, 3rd Edition: The caregiver interview form will be used to evaluate communication, socialization, and daily living skills of subjects to assess their overall adaptive

functioning. The items in the Vineland Adaptive Behavior Scale requires the caregiver to be familiar with the subject's day-to-day functioning in areas of communication, socializing, and daily living skills. As such, for subjects who reside independently, the rater who administers the assessment should determine if the caregiver, if he/she is available during the visit, has sufficient knowledge of the subject's day-to-day functioning to be able to complete the interview. If the caregiver is not familiar with the subject's day-to-day functioning skills, then the assessment should not be completed. The motor subdomain will be administered to those up to age 9 years. This assessment is an interview of the caregiver by a qualified rater (8). The semi-structured interviews will be recorded in a standardized manner.

Bayley Scales of Infant and Toddler Development Third Edition (Bayley-III): The comprehensive tool has 5 developmental domains, of which we will utilize 4: Cognitive Scale, which assesses attention to familiar and unfamiliar objects, looking for a fallen object, and pretend play, Language Scale, which focuses on recognition of objects and people, following directions, and naming objects and pictures, Motor Scale, which assesses gross and fine motor skills such as grasping, sitting, stacking blocks, and climbing stairs, and Social-Emotional Scale, which measures a child's ability to engage with others socially, self-calm and takes part in age-appropriate play. We will not make use of the Adaptive Behavior Scale to avoid duplication of the same information. Raw scores of successfully completed items are converted to scale scores and to composite scores. These scores are used to determine the child's performance compared with norms taken from typically developing children of their age (in months). The Bayley-III will be performed through 42 months of age.

Wechsler Abbreviated Scale of Intelligence Second Edition / Wechsler Preschool & Primary Scale of Intelligence Fourth Edition (WASI-II / WPPSI-IV): A test of intellectual functioning comprised of verbal and visual reasoning subtests as well as tasks of working memory and processing speed.

Stanford-Binet Fifth Edition (SB5): The Stanford-Binet test V is an examination meant to gauge intelligence through five factors of cognitive ability. These five factors include fluid reasoning, knowledge, quantitative reasoning, visual-spatial processing and working memory. Both verbal and nonverbal responses are measured. Each of the five factors is given a weight and the combined score is often reduced to a ratio known commonly as the intelligence quotient, or IQ. For children ages 2 to 5, use the early SB5.

Timed Up & Go Test (TUG): The Timed Up and Go Test (TUG) is a measure of mobility. Patients are asked to sit in a regular chair and upon command rise from the chair, walk at their normal pace to a line on the floor 10 feet (3 meters) away from the chair, return to the chair and sit down again. The time required by the patient to complete the assessment is measured and recorded. The TUG should be performed in triplicate at each visit and the best performance will be used for analyses. The TUG is administered by a Physician, a Physical Therapist, or designee familiar with the test. Every attempt should be made that the same assessor is administering the TUG in a given patient throughout the study. TUG will be administered to ambulatory patients in this Study.

Pediatric Evaluation of Disability Inventory-Computer Adaptive Test (PEDICAT): PEDI, originally published in 1992 by Haley et al. and revised as a computer adaptive test (CAT) – the PEDI-CAT, is a parent/clinician functional test that measures abilities in 4 content domains: daily activities, mobility, social/cognitive, responsibility. It will be completed by the caregiver with support from a qualified study center staff, for subjects younger than 20 years of age (9).

Pediatric Quality of Life Inventory (PedsQL)-Family Impact Module: Measures parent self-reported physical, emotional, social, and cognitive functioning, communication, and worry (10). The Module

also measures parent-reported family daily activities and family relationships. This assessment will be used in subjects between 2 and 18 years of age.

Overall Neuropathy Limitation Scale (ONLS): The scale was derived by modifying the Overall Disability Sum Score (ODSS) slightly to avoid the ceiling effect. Its inter-rater reliability was found to be high, as was its correlation with the ODSS (11). It is used to assess the limitations of subjects with immune-mediated peripheral neuropathies. It focuses on upper and lower limb functions and consists of a checklist for interviewing subjects. This scale will be used in subjects 18 years of age or older.

Pediatric CMT-specific Quality of Life Patient-reported Outcome Measure (pCMT-QOL PRO) and parent proxy (pCMT-QOL parent proxy): Measures patient-reported physical (symptoms, function, social activities) and social (feelings, cognition, and social skills) domains specific for children with CMT (12). This scale will be used in subjects 8 to 18 years of age.

Pediatric CMT-specific Quality of Life Parent-proxy Outcome Measure (pCMT-QOL [0 to 7 years parent-proxy]): Measure parent-reported physical (symptoms, function, social activities) and social (feelings, cognition, and social skills) domains specific for children with CMT (13). This scale will be used in subjects 7 years of age or younger.

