| Assessments | 
Clinical Assessments:
 
 • Electrophysiology • Nerve Conduction Studies (NCS) • Pulmonary Function Tests (PFTs) • Scoliosis series X-ray • Magnetic Resonance Imaging 
 1. Thigh and calf muscle without contrast 2. Brain without contrast 
Neuropsychological Assessments:
 
 • Vineland Adaptive Behavior Score, 3rd edition • Bayley Scales of Infant and Toddler Development-III • Wechsler Abbreviated Scale of Intelligence Second Edition / Wechsler Preschool & Primary Scale of Intelligence Fourth Edition (WASI-II / WPPSI-IV) • Stanford-Binet V (SB5) 
Physical Therapy Assessments:
 
 • PEDICAT • CMTPedS for subjects 5 to 17 years of age • CMTInfS (< 4 years old) • CMTNSv2 for subjects >18 years of age • CMT-FOM for subjects > 18 years of age • Timed Up and Go Test (TUG) 
Questionnaires:
 
 • PedsQL (2-18 years) • ONLS (18 years and older) • pCMT-QOL PRO (8-18 years) • pCMT-QOL parent proxy (8-18 years) • pCMT-QOL parent proxy (0-7 years) • CMT Health Index (CMTHI) for >18 years of age |

| | |
|-----------------------------------|---|
| | 
Exploratory Assessments:
 
• Blood collection for exploratory biomarker• Wearable devices• Optional skin biopsy |
| STATISTICAL CONSIDERATIONS | 
The sample size of 20 subjects is expected to provide sufficient insights into the natural history of individuals with CMT4J, a rare disease, to provide exploratory and descriptive results and guide the design of future studies of CMT4J. No formal sample size estimation was performed for this study. Parametric and non-parametric tests will be used to analyze possible associations between clinical, radiographic, and laboratory data. The tests will be selected based on the question being asked of the database. This database will be used to analyze multiple medical issues among subjects with confirmed CMT4J.
 |

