| CMT Specific Scales 
 - CMTPedS for subjects 5-17 years of age - CMTInfs < 4 years of age - CMTNSv2 for subjects >18 years of age - CMT-FOM for subjects > 18 years of age - CMT Health Index (CMTHI) for >18 years of age | Validated clinical outcome measures to monitor progression of sensorimotor function, disease-burden and quality of life in CMT subjects | No known risks. May experience mild frustration or fatigue with challenging tasks. May experience mild psychological discomfort when completing rating forms on topics including school performance, mood, and quality of life. | Subjects allowed to take breaks. |
| Electrophysiology Nerve Conduction Studies (NCS) | Evaluates sensory and motor responses in the upper and lower extremities including distal latency, amplitude and conduction velocity. | Risk of discomfort with muscle contraction from stimulation. Mild muscle soreness and fatigue. Discomfort from staying still during the procedure. | Procedure expectations will be communicated with the subjects and time will be given between stimulations. |
| Magnetic Resonance Imaging of the thigh and calf muscle without contrast | MRI scan of the thigh and calf muscle to characterize the structural abnormalities in CMT4J. | Risk for injury from the MRI magnet if present: pacemakers or other implanted electrical devices, brain stimulators, some dental implants, aneurysm clips, metallic prostheses, permanent eyeliner, implanted delivery pump, magnetic devices (such as | Individuals are screened to ensure MRI safety procedures are met before a scan Hearing protection for risk of hearing damage |
| Brain MRI without contrast | MRI scan of the brain. | | |

| | | | |
|---|--|---|--|
| | | magnetic spine growing rods) or shrapnel fragments. Risk of discomfort from laying on hard surface or anxiety if fear of confined spaces or loud noises | |
| Neuropsychological and Physical therapy Assessments | A series of performance-based activities to assess psychomotor functioning and quality of life. This includes: 
 • Vineland Adaptive Behavioral Scale • PEDICAT • PedsQL • ONLS • pCMT-QOL • Bayley-III, • WASI-II, WPPSI-IV • Stanford-Binet test V • TUG | Discomfort or psychological stress and tiredness. | Subjects allowed to take breaks. |

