APPENDIX 1: SCHEDULE OF EVENTS

| Study Day | Screening | Baseline | Month 12 | Month 24 |
|---|------------------|------------------|------------------|------------------|
| Windows | | (± 4 wks) | (± 4 wks) | (± 4 wks) |
| Informed Consent | X | | | |
| Medical Information | | X | X | X |
| Demographics | | | | |
| Medical History | | X | X | X |
| Family History | | X | | |
| CMT4J Diagnosis and History | | X | | |
| Clinical Procedures | | | | |
| Inclusion/Exclusion Criteria | X | | | |
| Vital Signs ^a | | X | X | X |
| Height and Weight | | X | X | X |
| Physical Exam ^b | | X | X | X |
| Neurological Exam ^c | | X | X | X |
| Urine Pregnancy (for female subjects) ^d | | X | X | X |
| Blood Collection for Future Exploratory Analysis ^e | | X | X | X |
| Skin biopsy (optional, any visit, only once) | | X | X | X |
| Adverse Events | | X | X | X |
| Concomitant Medications | | X | X | X |
| CMT Scales* | | | | |
| CMTpedS ^f | X | X | X | X |
| CMTInfS ^g | X | X | X | X |
| CMTNSv2 ^h | X | X | X | X |
| CMT-FOM ^h | X | X | X | X |
| CMT Health Index (CMTHI) ^h | X | X | X | X |
| Clinical Studies | | | | |
| Thigh and Calf MRI without contrast | | X | X | X |
| Brain MRI without contrast | | X | X | X |
| Nerve Conduction Study (NCS) ⁱ | | X | X | X |
| Pulmonary Function Test (PFT) ^j | | X | X | X |
| Scoliosis Series X-ray ^k | | X | X | X |
| Neuropsychological and Physical Therapy Assessments | | | | |
| Vineland Adaptive Behavior Scale | | X | X | X |
| PEDICAT ^l | | X | X | X |
| Bailey III | | X | X | X |
| WASI-II or WPPSI-IV | | X | X | X |
| Stanford Binet – V | | X | X | X |
| Timed up and go (TUG) | | X | X | X |
| Wearable devices | X | X | X | X |
| Questionnaires | | | | |
| PedsQL ^m | | X | X | X |
| Overall Neuropathy Limitation Scale (ONLS) (18 years and older) | | X | X | X |
| pCMT-QOL PRO (8 to 18 years) | | X | X | X |
| pCMT-QOL (8 to 18 years parent-proxy) | | X | X | X |
| pCMT-QOL (0 to 7 years parent-proxy) | | X | X | X |

-
- ^a Temperature, pulse, blood pressure measured in one arm or leg after the patient has been seated for ~ 5 minutes.
 - ^b Exam of heart, lungs, abdomen, back, and extremities; height and weight; head circumference
 - ^c Includes evaluation of cranial nerves, muscle tone, muscle strength, sensation, gait, coordination and deep tendon reflex testing, handheld dynamometry

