 - ^d Urine pregnancy test for females of child-bearing potential. Results of urine pregnancy test must be reviewed and confirmed to be negative prior to proceeding with any assessments involving radiation. If a urine pregnancy test is positive, it must be confirmed by a serum pregnancy test. If the subject's urine or serum pregnancy test is positive, assessments involving radiation should not be performed.
 - ^e With subject consent, blood and blood products may be stored long-term for exploratory purpose; these samples will be maintained for up to 10 years
 - ^f Subjects aged 5 to 17 years 11 months (less than 18 years)
 - ^g Subject < 4 years of age
 - ^h Subjects aged 18 years and older
 - ⁱ Ideally, performed on the left arm and leg, the same limbs will be assessed at each visit
 - ^j Subjects older than 5 years of age based on the physiotherapist's assessment of subject's compliance and/or ability to follow instructions
 - ^k Thoracic and lumbar spine
 - ^l Subjects < 20 years
 - ^m Subjects 2 to 18 years
- *Video capture will be used for some parts of the CMT scales.

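### No CMT-specific motor scale is assigned to children aged 4 to under 5, because CMTInfS stops below 4 and CMTPedS starts at 5

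*Protocol*

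**What the plan says.** Inclusion criterion 1 (Section 2.2) sets no age limit. The two paediatric CMT motor scales are assigned as follows.

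- **CMTPedS.** Section 3.1: "This scale will be used for subjects aged 5 to 17 years 11 months (less than 18 years"). Synopsis: "CMTPedS for subjects 5 to 17 years of age". Appendix 1, footnote f: "Subjects aged 5 to 17 years 11 months (less than 18 years"). The Section 4 risk table gives the same range.
- **CMTInfS.** Synopsis: "CMTInfS (< 4 years old"). Section 4 risk table: "CMTInfs < 4 years of age". Appendix 1, footnote g: "Subject < 4 years of age". Section 3.1 states no explicit band. It says that CMTPedS scores vary widely below age 4 and that CMTInfS may be more sensitive at age 3.

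CMTNSv2, CMT-FOM and CMTHI are adult instruments (Section 3.1; Appendix 1, footnote h).

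The Appendix 1 columns read "Study Day | Screening | Baseline | Month 12 | Month 24". Both paediatric scales are marked in all four, for example "CMTInfS ^g | X | X | X | X".

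**The concern.** One band ends at the fourth birthday and the other begins at the fifth. The rationale in Section 3.1 supports a boundary at 4, because it is below that age that CMTPedS is said to be unreliable. It gives no reason for CMTPedS to start a year later.

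Section 1.4 makes the evaluation of candidate motor outcome measures an objective, and Section 3.1 presents CMTInfS as a means of learning how fast the disease progresses at its earliest stages. A site that follows the protocol exactly collects no CMT motor score at age 4. This is a data-collection rule, so no analysis plan can repair it later. A child may lose the baseline, lose the final score, or have a hole in the middle with a different scale on each side.

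**Working it through.** **Inputs**

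- Bands: CMTInfS below 4 and CMTPedS 5 to under 18 (synopsis, Section 3.1, Section 4 risk table, Appendix 1 footnotes).
- Annual time points: Baseline, Month 12, Month 24 (Appendix 1).
- Possible extension of up to 60 months, if feasible (synopsis, Study Duration).
- About 20 subjects (Section 10).
- Assumptions: the band follows age at visit; visits fall at nominal times (shifts within the ±4-week window are not modelled); Screening falls in the same year of age as Baseline.

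**Step 1. Uncovered ages.** In completed months, CMTInfS covers 0 to 47, CMTPedS 60 to 215, and the adult scales 216 onwards. The uncovered ages are exactly 48 to 59 months. Under the Section 3.1 and Appendix 1 ranges there is no other gap.

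**Step 2. Initial 24 months, for the entry years that meet the gap**

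| Age at entry | Baseline | Month 12 | Month 24 | Same-scale annual intervals |
|---|---|---|---|---|
| 2 to <3 | CMTInfS | CMTInfS | none | 1 of 2 |
| 3 to <4 | CMTInfS | none | CMTPedS | 0 of 2 |
| 4 to <5 | none | CMTPedS | CMTPedS | 1 of 2 |

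- Annual time points with a scale: 2 + 2 + 2 = 6 of 9.
- Adding Screening: 3 + 3 + 2 = 8 of 12 visits. Screening adds no annual interval, and a child entering at 4 is unscored there too.
- Same-scale annual intervals: 1 + 0 + 1 = 2 of 6.

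**Step 3. The same entry years with bands that meet**

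- Cut-off 4: Inf-Inf-Ped, Inf-Ped-Ped, Ped-Ped-Ped. Visits 12 of 12; intervals 1 + 1 + 2 = 4 of 6.
- Cut-off 5: Inf-Inf-Inf, Inf-Inf-Ped, Inf-Ped-Ped. Visits 12 of 12; intervals 2 + 1 + 1 = 4 of 6.

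**Step 4. If annual visits continue to Month 60.** Entry years 0 to <5 each meet the gap at one of six annual time points. Same-scale intervals, for entry at 0, 1, 2, 3 and 4:

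- Current bands: 3 + 3 + 3 + 3 + 4 = 16 of 25.
- Cut-off 4: 4 + 4 + 4 + 4 + 5 = 21 of 25.
- Cut-off 5: 4 + 4 + 4 + 4 + 4 = 20 of 25.

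**Step 5. How many children.** The protocol gives no age distribution. As an assumption, take entry ages uniform from 0 to U years, with 20 subjects. The expected number affected is 20 × 3/U over 24 months and 20 × 5/U over 60 months.

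| U (years) | 24 months | 60 months |
|---|---|---|
| 18 | 3.3 | 5.6 |
| 25 | 2.4 | 4.0 |
| 40 | 1.5 | 2.5 |
| 60 | 1.0 | 1.7 |

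**Step 6. Study-level share over 24 months.** Twenty subjects at three annual time points give 60 subject-visits and 40 intervals.

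- Lost visits: 1.0 to 3.3 of 60, or 1.7% to 5.6%.
- Intervals gained by closing the gap: two per three affected children, so about 0.7 to 2.2 of 40.

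**Step 7. If the band were instead fixed at entry.** Only entry at 4 to <5 is affected: 20/60 = 0.3 to 20/18 = 1.1 children. Each would have no scale at any of the three annual time points, so the expected loss is again about 1.0 to 3.3 visits.

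**The case against.** The bands agree wherever they appear, so the protocol does not contradict itself. It also limits other tests by age: Bayley-III through 42 months, pulmonary function only above 5 years, the scoliosis X-ray not above 17. The gap could be deliberate. That possibility stands, and it is why stating a reason is an acceptable answer; the present text gives none.

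The affected share is small. The 8 of 12 and 2 of 6 counts cover only the entry years that meet the gap, and Step 6 shows how little of the whole study that is. Uniform entry from birth probably overstates it: Section 2.1 requires a prior, genetically confirmed diagnosis and Section 1.1 describes frequent misdiagnosis, so there may be no such children. The 60-month counts depend on an extension that Appendix 1 does not schedule. All of this limits the size of the problem but does not remove it.

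Children of 4 are not unmeasured. PEDI-CAT, the Vineland motor subdomain, the pCMT-QOL parent proxy, TUG if ambulatory, dynamometry, nerve conduction and muscle MRI all apply. Children entering below 2 also keep CMTInfS at all three time points in the first 24 months. That is a fair limit on the harm. None of these measures, however, is a CMT-specific motor scale: PEDI-CAT and Vineland rest on the caregiver, and pCMT-QOL measures quality of life.

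Section 3 lets sites omit an assessment that a subject cannot perform. That permits omission but assigns nothing at age 4.

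Lastly, closing the gap does not remove the change of scale. Two of the six intervals still cross scales under either cut-off, and the protocol does not say how well either scale works at age 4.

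**Conclusion.** The point holds and should be fixed. The gap at age 4 to under 5 follows directly from the text and is unexplained. In the initial 24 months, if the band follows age at visit, every child entering at 2 to under 5 loses the scale at one annual time point: a child entering at 3 has no same-scale annual change, and one entering at 4 has no baseline.

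The gap itself is certain; its size is not. The figure of 1.0 to 3.3 children of 20 rests on assumed uniform entry ages and may be too high. All analyses are exploratory (Section 10), so no confirmatory test is at risk. This is a small loss of data that cannot be made good afterwards, in a study of about 20 subjects that is meant to evaluate motor outcome measures.

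**What to change.** 1. Make the CMTInfS and CMTPedS bands meet at a single cut-off, 4 or 5, with whichever scale the sponsor confirms is suitable at age 4. Use it in the synopsis, Section 3.1 (adding the missing explicit CMTInfS band), the Section 4 risk table and Appendix 1 footnotes f and g. If the gap is intended, state the reason instead.
2. State that the band follows age at visit.

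The counts do not favour one cut-off over 24 months. Over a possible 60 months they differ by one interval (21 against 20 of 25), so suitability at age 4 should decide.

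The cost is a wording change in four places and one extra scale at the few visits that now have none. Section 3.1 puts CMTInfS at 20 minutes and gives no time for CMTPedS. The drawback is that scores from 4-year-olds may be noisier.
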